9.2.3 Interim and Final Qualitative Analyses

The goal of coding these data is to facilitate the identification of concepts regarding the understanding of and adherence to PPP measures that are most important and relevant to participants who use oral retinoid therapy. The coding process identifies and categorizes WCBP and HCP's expressions into concepts of relevance aligned with the established coding frame. Coders will review each transcript to identify text that includes concept expression data and tag selected text with individual codes.

The codes will be organized using overall categorization following the PRECEDE–PROCEED model phases which are established at the beginning of the coding process and refined/expanded during coding using a standardized dictionary of terms.

Both deductive and inductive approaches will be used.

The deductive coding approach allows researchers to apply findings from other phases of the research to the coding framework, based on the topics included in the discussion guide. The deductive coding framework will be developed using the standardized dictionary of terms which will then be adapted to the project as needed. This standardized dictionary is continually updated to reflect the most recent research conducted across all PCS projects and ensures consistency in qualitative data analysis.

On the other hand, inductive coding is a technique whereby codes are derived from the data as concepts and ideas naturally emerge during coding. This combined approach helps to ensure the coding structure necessary for the content analysis of this type of qualitative data. Further, it provides an opportunity to thematically analyse new concepts and ideas as they emerge spontaneously from the data.

Inter-coder agreement will be regularly assessed throughout the coding process and dual coding will take place on a 20% sample of transcripts, with any revised or new codes retroactively applied to already coded transcripts. In addition, code saturation will be assessed after each interview by comparing the codes and code's definitions (e.g., reasons for not adhering to PPP measures, preferred methods of communication) used and elicited during each interview, following analysis of the coding performed in MAXQDA 2022, to evaluate whether the number of interviews conducted is sufficient to comprehensively characterize the participants' experiences with PPP measures.

9.2.3.1 Code Saturation and Code Meaning

Saturation refers to the point in qualitative research where new data collection or analysis ceases to yield additional insights or information, indicating that the exploration of the research topic has reached a point of completeness (16). It signifies that researchers have thoroughly explored and understood the key concepts and themes related to their study. At this stage, the redundancy of information becomes apparent, and further data collection may not contribute substantially to the richness or depth of the findings.

Various definitions of saturation may be applicable depending on the qualitative study design, methodologies implemented and objectives (16).

Considering the coding methodology implemented in this study, saturation will be defined by the achievement of “code saturation” (14): this occurs when the codebook has stabilized, indicated by a low percentage or absence (<10% of total codes in the codebook) of new codes or changes to the code’s definition.

Additionally, a “code meaning” (14) assessment will also be conducted to explore the dimensions contained within each of the codes of the codebook. “Code meaning” will be monitored by compiling the various individual meanings reported by participants during the interviews attributed to the codes used. In this approach, from the coding of the initial interview, and throughout subsequent interviews, new aspects, dimensions, or nuances of already documented codes will be captured and summarized, according to the participant-reported experiences, thoughts and opinions. The “code saturation” and “code meaning” approaches are further in the Qualitative Analysis Plan (Annex 4. Qualitative Analysis Plan) to present how these will be performed to monitor saturation related to the experiences of participants recruited from different countries and to the experiences of adult WCBP and parents, guardians or legal caregivers of adolescent WCBP using different oral retinoids.

9.2.3.2 *Interim Analysis and go/no-go decision*

Interim analysis will be conducted after 50% of the total planned interviews have been completed (per country and molecule)².

The interim analysis will seek to evaluate whether the study sample sizes are adequate for reaching code saturation among participants recruited from each of the four study countries (France, Germany, Poland and Spain) and between the three oral retinoid molecules (isotretinoin, acitretin, and alitretinoin) used by adult WCBP and two oral retinoid molecules used by adolescent WCBP (isotretinoin and acitretin). A decision to expand recruitment to potential additional regions of Europe and/or increasing samples for specific oral retinoids will be taken based on the interim analysis’ findings.

To assess the diversity and representativeness of experiences reported across European countries, the challenges and barriers of adhering to PPP measures highlighted by adult WCBP and parents, guardians or legal caregivers of adolescent WCBP from each of the four study countries (France, Germany, Poland and Spain) will be described and compared between the study sample. Participants will also be asked to rank the top five most important

² The interim analysis and reporting is planned to take place between October to December 2025, as described in section 6.

[figure not shown]
barriers and challenges to adhering to PPP measures according to their experience which will further serve as basis to assess cross-country and region similarities and/or differences.

This ranking will serve as the main basis to assess cross-country and region similarities and/or differences. A comparison of the most important barriers/challenges with a cut-off score of three common barriers will be used to conclude sufficient similarities between geographical scope. That is, if amongst the five most important barriers and challenges identified, at least three are common to the four included study countries (France, Germany, Poland and Spain), it will be concluded that there are similarities that are sufficient amongst the countries included in the scope of the study to prevent the need to add an additional country for the subsequent portion of the study.

If this is not the case, triangulation of the qualitative findings related to barriers/challenges ranked by participants with existing literature (either peer-reviewed or from reports or assessments performed by institutional country agencies) identified following a narrative review of barriers to adhering to PPP measures highlighted by adult WCBP and parents, guardians or legal caregivers of adolescent WCBP in the Nordic/northern European regions will be performed. The triangulation will seek to confirm if the diversity of the qualitative findings collected is able to cover known barriers and challenges to adhering to PPP measures previously identified in northern European countries.

If the most important barriers identified compare across all included countries, no additional country will be included for the subsequent portion of the study. If this is not the case, a recruitment strategy including samples representative from other European regions (e.g. Nordic countries) will need to be considered. Additional details are presented in the Qualitative Analysis Plan (Annex 4. Qualitative Analysis Plan). The decision-making plan for assessing if the study data is representative of the diversity of barriers/challenges reported across European regions, including northern Europe, is presented in **Figure 3**.

Figure 3. Decision flow for conclusions on the representativeness of the diversity of barriers/challenges reported across European regions

Similarly, to assess the consistency of barriers and challenges to adherence between the three oral retinoid molecules (isotretinoin, acitretin, and alitretinoin) used by adult WCBP and two oral retinoid molecules used by adolescent WCBP (isotretinoin and acitretin), code

Based on Template No.: RWI_TP_EPI0016
 Revision 1

Reference: RWI_WI_EPI0005

Effective Date: 15Jun2018

saturation between molecules will be assessed and compared. The interim analysis will involve the coding of the transcripts and assessment of code saturation and code meaning, as described in section 9.2.3.1. Reviewing the frequency and consistency of codes to determine if new codes continue to emerge or if the existing codes sufficiently capture the data will determine whether additional samples for specific molecules (e.g. acitretin) will need to be increased to achieve code saturation per molecule. Additional details are presented in the Qualitative Analysis Plan (Annex 4. Qualitative Analysis Plan).

The results of the interim analysis will be documented in an interim report, which will include a summary of the data collected to date, an assessment of code saturation, and recommendations for any adjustments to the study protocol. The interim analysis will ensure that the study remains on track to achieve its objectives and that the data collected is robust and comprehensive. The interim analysis report will be shared with the Reference Member State (RMS) for review.

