The data analysis for this study will adhere to a Qualitative Analysis Plan (Annex 4. Qualitative Analysis Plan). Sociodemographic and clinical variables characterizing participants will be summarized. Continuous variables will be summarized with mean,

standard deviation, minimum, and maximum values. Categorical variables will be described in total numbers and percentages per category.

The qualitative data analysis will employ thematic analysis methods using a qualitative analysis software (MAXQDA 2022). The analysis will be guided by the PRECEDE-PROCEED implementation science framework, which is divided into PRECEDE and PROCEED phases, and aids in systematically assessing various aspects of the study topic. Participants' experiences with oral retinoids PPP measures will be categorized using both deductive and inductive coding approaches.

Deductive coding involves applying findings from other phases of the research to the coding framework, adapted from a standardized dictionary of terms. Inductive coding derives codes from emerging concepts during analysis, contributing to thematic analysis. Inter-coder agreement will be regularly assessed, and dual coding on 20% of the sample will ensure consistency. Code saturation, achieved at the moment where the codebook stabilizes and new codes or code's nomenclatures become increasingly rare as interviews are conducted, will be assessed after each interview by comparing the codes and code's definitions (e.g., reasons for not adhering to PPP measures, preferred methods of communication) used and elicited during each interview, following analysis of the coding performed in MAXQDA 2022, to determine the sufficiency of interviews in capturing participants' experiences. The concept saturation approach will be detailed in the Qualitative Analysis Plan to ensure rigor and validity in the study.

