9.1.1 Sample Size and Inclusion/Exclusion Criteria

Qualitative studies do not involve power estimates for sample size, as they rely on establishing saturation to determine when data collection is complete. Saturation in this study will be defined by the achievement of “code saturation” (14). Previous studies involving the assessment of code saturation observed that approximately 9 interviews were sufficient to achieve saturation (14). Sample size recommendations are based on this evidence, while also considering the various subgroups of interest involved in the study and

the anticipated diversity of experiences to be comprehensively captured. Additional information about the adequacy of the sample size and the saturation approach considered for this study is provided in section 1.1.1.1 and further detailed in the Qualitative Analysis Plan, which can be accessed in Annex 4. Qualitative Analysis Plan.

Included oral retinoid therapies in this study are acitretin, isotretinoin and alitretinoin. The target population will include a sample of

- HCPs who prescribe or dispense oral retinoid therapy;
- WCBP who currently or recently used oral retinoid therapy, and;
- Parents of adolescent WCBP who currently or recently used oral retinoid therapy (except alitretinoin).

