9.1.1.1.2 Exclusion Criteria for HCPs Prescribing/Dispensing Oral Retinoid Therapy

HCPs will be excluded from this study if meeting the following criteria:

- Being an inactive and retired HCP / allied HCP at the time of the interviews;
- Having a conflict of interest with the study (i.e., being employed by regulatory bodies, and/or pharmaceutical companies).

9.1.1.2 *Inclusion/Exclusion Criteria for WCBP (aged 18-49) and Parents, Guardians, or Caregivers of Adolescent WCBP*

9.1.1.2.1 *Inclusion Criteria for WCBP (aged 18-49) and Parents, Guardians, or Caregivers of Adolescent WCBP*

As shown in Table 2 below, between 25-28 WCBP and 10 parents, guardians or caregivers of adolescent WCBP per country (France, Germany, Poland, and Spain) will be targeted, if meeting the following inclusion criteria described below:

For isotretinoin (n=15 per country, 60 WCBP across all countries):

- Being female sex aged 18 to 49;
- Currently or recently (within the last 6 months) using isotretinoin;
- Willing/consent to participate in this study.

For acitretin (n=5 per country, 20 WCBP across all countries):

- Being female sex aged 18 to 49;
- Currently or recently (within the last 6 months) using acitretin*;
- Willing/consent to participate in this study.

For alitretinoin (n=5-8 from France, Germany, and Spain, 0 from Poland, 20 WCBP across all countries):

- Being female sex aged 18 to 49;
- Currently or recently (within the last 6 months) using alitretinoin*;
- Willing/consent to participate in this study.

Parent, guardians, or legal caregivers of Adolescent WCBP (n=10 per country)

- Parent, guardian or legal caregiver of adolescent WCBP aged 13 to 17 who are currently or recently (within the last 6 months) using isotretinoin or acitretin;
- Willing/consent to participate in this study.

Table 2. Target WCBP Samples across oral retinoid medication and country

Target country	Target WCBP samples to be recruited*			
	Isotretinoin	Alitretinoin (Min/Max)	Acitretin	Total (Min/Max)
France	15	5 - 8	5	25-28*

Germany	15	5 - 8	5	25-28*
Poland**	15	N/A**	5	20
Spain	15	5 - 8	5	25-28*
Total	60	20	20	100

*Note that this is a target number which may change depend on success of recruitment at local level. Country-specific targets may vary to account for the alitretinoin variability per country, but the overall sample will be of 100 WCBP globally.

Table 2 does not include n=10 parents, guardians, or caregivers of adolescent WCBP from each country.

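### The <10% code-saturation rule in section 9.2.3.1, checked after each interview, can be met while new codes keep arriving at a constant rate, so it can falsely reassure at the molecule interim

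*Protocol*

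**What the plan says.** Protocol section 9.1.1 gives saturation the place of a power calculation, saying that qualitative studies "rely on establishing saturation to determine when data collection is complete". It adds that earlier work needed about 9 interviews.

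Section 9.2.3.1 supplies the numerical criterion: a stabilised codebook, "indicated by a low percentage or absence (<10% of total codes in the codebook) of new codes". The sentence continues so that the numerator consists "of new codes or changes to the code’s definition".

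Section 9.2.3 sets how often this is checked: "code saturation will be assessed after each interview by comparing the codes". It also shows that the codebook is not empty at the first interview: "The deductive coding framework will be developed using the standardized dictionary of terms".

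The Abstract (Data Analysis) describes what the rule is meant to capture: "new codes or code's nomenclatures become increasingly rare as interviews are conducted".

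Section 9.2.3.2 places the interim at half of the planned interviews per country and molecule. It uses code saturation to decide whether the sample for a particular molecule must be increased. Detail on monitoring by country and molecule is left to the Qualitative Analysis Plan (Annex 4), which is not shown.

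**The concern.** The Abstract's idea of saturation is a falling rate of new codes. The criterion in section 9.2.3.1 is a ratio to a codebook that starts part-filled and only grows. Such a ratio falls even when discovery does not slow, so passing the rule is not evidence that discovery has slowed.

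Two outputs depend on it: the interim decision on enlarging the acitretin or alitretinoin sample, and the final statement that the interviews captured participants' experiences. These are the two smallest molecule groups of adult women (20 each), and the protocol itself expects them to be hard to recruit. A rule that passes by construction is least useful there.

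**Working it through.** **Inputs from the protocol.** The threshold is <10% of total codes (9.2.3.1). The check follows each interview, with deductive codes present at the start (9.2.3). Adult women: 60 isotretinoin, 20 acitretin, 20 alitretinoin (9.1.1.2.1, Table 2). The interim falls at 50% per molecule (9.2.3.2), so 0.5 × 20 = 10 interviews each for acitretin and alitretinoin.

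**The plan's own figures.** The total reproduces: 60 + 20 + 20 = 100. The figure of about 9 interviews comes from a cited study without inputs and cannot be re-derived.

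**Assumptions.** The protocol does not give D, the deductive codes at the start, or a, the new codes per interview. I hold a constant, meaning that discovery never slows. I also let each molecule have its own codebook, which favours the rule.

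**Per-interview reading, new codes only.** After interview k the book holds D + a·k codes, of which a are new:

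share(k) = a / (D + a·k), which is below 10% when k > 10 − D/a.

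- D = 0: the share is 1/k whatever a is. This gives 20% at k = 5, exactly 10.0% at k = 10 (not yet a pass), 9.1% at k = 11 and 5% at k = 20.
- D > 0, k = 10: a/(D + 10a) < 0.10 is the same as 10a < D + 10a, that is, D > 0. One deductive code is enough for a pass at the molecule interim.
- Illustrations: D = 20, a = 5 first passes at interview 7. D = 30, a = 5 first passes at interview 5.

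To stay at or above 10%, the codebook must grow by a factor of at least 1/0.9 = 1.111 per interview: 2.9-fold over 10 interviews and 8.2-fold over 20. Only accelerating discovery keeps failing the rule.

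**With definition changes.** If they equal the new codes in number, the share is 2a/(D + a·k), below 10% when k > 20 − D/a.

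- D = 0: first pass at interview 21.
- D = 30, a = 3: exactly 10.0% at interview 10 (6/60), first pass at interview 11.
- At the 10-interview interim a pass needs D > 10a. At the full 20 interviews it again needs only D > 0.

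**With a five-interview window.** The share is 5a/(D + a·k), below 10% when k > 50 − D/a.

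- D = 0: 5/k, exactly 10% at 50, so the first wave to pass ends at interview 55.
- D = 30, a = 3: the first wave to pass ends at interview 45.
- Within a 20-interview molecule group a pass needs D > 30a.

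**The case against.** The strongest reply is that section 9.2.3.1 states no window for the numerator. Checking after each interview fixes how often one looks, not over how many interviews new codes are counted, and section 9.2 has data reviewed between waves of about five. With a five-interview window and few deductive codes, the false pass lies beyond the 20-woman groups. This stands as a limit. The per-interview count is the more natural reading of section 9.2.3, and the between-wave review in section 9.2 concerns changes to the interview questions. Definition changes also count and delay the pass, as shown.

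Four stronger readings that a reader might infer are not supported:

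- *New codes from a rare molecule are diluted by codes from 120 HCPs and 60 isotretinoin users.* The protocol does not state a pooled denominator. Section 9.2.3.2 speaks of saturation per molecule, and section 9.2.3.1 sends the monitoring detail to the Qualitative Analysis Plan.
- *The rule ends data collection early.* Recruitment stops at target numbers (9.1.2.1, 9.1.2.2.2). The sentence in 9.1.1 is a general remark about qualitative studies.
- *The rule decides whether a country is added.* The main basis is the ranking of the top five barriers with a cut-off of three in common, followed by triangulation with the literature (9.2.3.2).
- *The plan has no other way to see an inadequate sample.* It also assesses code meaning and reviews whether new codes continue to emerge. Those checks carry no threshold, so the <10% rule remains the only numerical criterion.

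**Conclusion.** The point holds as a defect in a rule that the protocol fixes, not as a complaint about detail left to the analysis plan. On the per-interview reading, constant discovery meets the <10% criterion by interview 11 at the latest, and at the 10-interview acitretin or alitretinoin interim for any non-empty deductive codebook. Neither result needs a value for D or a. How much earlier a pass comes does depend on them.

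The conclusion rests on a per-interview numerator and on counting new codes alone. As many definition changes as new codes would move the D = 0 pass to interview 21. A five-interview window would move it beyond 50 interviews. The consequence is limited to a falsely reassuring interim decision on molecule samples and a falsely reassuring final saturation statement.

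**What to change.** In section 9.2.3.1, and to match in the Qualitative Analysis Plan:

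1. Define saturation separately in each stratum judged: respondent type by country, and respondent type by molecule.
2. Numerator: new codes plus changed definitions in the last five interviews of that stratum, in order of conduct. Order of conduct is needed because waves are per country and molecule strata span countries. Count a code as new at its first use in the stratum, whether it came from the dictionary or from the data.
3. Denominator: codes actually elicited in that stratum before those five interviews, excluding unused dictionary codes.
4. Cover understanding, perception, barrier and facilitator codes, to match objectives P1 to P3.
5. Keep <10%. Report *not assessable* where a stratum has fewer than 10 interviews (for example parents by country at the interim, 5 of 10) and *not reached* where the criterion fails.

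Under constant discovery with m earlier interviews, the new-code share is 5a/(a·m) = 5/m, and definition changes only raise it. For a complete 20-interview stratum this is 5/15 = 33.3%, and for 50 interviews 5/45 = 11.1%, so the rule cannot pass in strata of 50 or fewer. It still can in a larger pooled stratum: for all 60 isotretinoin users, 5/55 = 9.1%.

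The cost is wording and a small tabulation from the coding software. The downside is that some small strata will be reported as not saturated or not assessable.

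### The interim comparison of code saturation between molecules shows whether each had enough interviews, not whether their users share barriers, so it cannot support a statement on consistency

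*Protocol*

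**What the plan says.** Section 9.2.3.2 (interim analysis and go/no-go decision) gives the aim of the molecule comparison: "Similarly, to assess the consistency of barriers and challenges to adherence between the three oral retinoid molecules" used by adults, and between the two used by adolescents. The measure follows in the same sentence: code "saturation between molecules will be assessed and compared".

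Section 9.2.3.1 defines code saturation: "this occurs when the codebook has stabilized", which is "indicated by a low percentage or absence (<10% of total codes in the codebook) of new codes or changes to the code" definitions.

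Back in section 9.2.3.2, a further review is described: "Reviewing the frequency and consistency of codes to determine if new codes continue to emerge or if the existing codes sufficiently capture the data". Its stated result is to determine "whether additional samples for specific molecules (e.g. acitretin) will need to be increased to achieve code saturation per molecule".

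For countries, the same section uses another kind of measure. Participants rank their five most important barriers, and "This ranking will serve as the main basis to assess cross-country and region similarities and/or differences". A threshold is attached: "A comparison of the most important barriers/challenges with a cut-off score of three common barriers will be used to conclude sufficient similarities", meaning at least three of the top five are common to the four study countries.

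**The concern.** The aim is about similarity of content: do users of isotretinoin, acitretin and alitretinoin meet the same obstacles? The named measure is about completeness: have new codes stopped appearing? The second does not answer the first. The paragraph opens as a parallel to the country comparison, but it replaces the content ranking with saturation and states no overlap criterion.

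Differences between molecules are plausible on the protocol's own facts. Table 1 gives three years of post-treatment contraception and testing for acitretin and one month for the other two. Section 9.4.4.1 says acitretin and alitretinoin are prescribed more often to older women and expects perceptions to vary. Section 9.2.2.2 intends to group barriers by specific oral retinoid in support of targeted actions. The interim report goes to the Reference Member State, so a consistency statement in it that rests on saturation alone would carry weight it has not earned.

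**Working it through.** There is no sample size, power or alpha to reproduce. The check is whether the measure responds to the thing it is meant to assess.

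**Inputs from the protocol**
- Planned adults by molecule (Table 2): isotretinoin 60, acitretin 20, alitretinoin 20.
- Interim at 50% of planned interviews, per country and molecule (section 9.2.3.2): 0.5 × 60 = 30, 0.5 × 20 = 10, 0.5 × 20 = 10.
- Saturation criterion (section 9.2.3.1): new or changed codes below 10% of total codes.

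**Assumptions, not in the protocol**
- Each molecule has 30 possible codes, each raised in an interview with probability p = 0.3, independently.
- The criterion is read per interview: codes new at the last interview, divided by that molecule's codes so far.
- Changes of definition are ignored.
- Overlap is codes seen in both molecules divided by codes seen in either.

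**Closed form for one molecule**
- Expected codes seen after n interviews = 30 × [1 − (1 − p)^n]. For n = 10: 30 × (1 − 0.7^10) = 29.2.
- Expected new codes at interview n = 30 × p × (1 − p)^(n−1). For n = 10: 30 × 0.3 × 0.7^9 = 0.36.
- Ratio at n = 10: 0.36 / 29.2 = 1.2%, well under 10%. At n = 30 it is practically zero.

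Neither formula contains anything about the other molecule. Under this reading the saturation result cannot depend on whether barriers are shared.

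**Simulation (3,000 runs per row, 30 against 10 interviews)**

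| True sharing of barriers | Both molecules saturated | Mean overlap of codes observed |
|---|---|---|
| None | 99.5% | 0 |
| Half of each molecule's codes | 99.6% | 0.33 |
| All | 99.3% | 0.97 |

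The saturation column is flat to within simulation error, while the true overlap runs from none to complete.

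**Does the rest of the paragraph supply a content comparison?**
- The review of code frequency and consistency is tied to whether new codes still emerge, and its only stated consequence is more interviews for a molecule.
- Code meaning (section 9.2.3.1) explores the dimensions within each code and is to be monitored by country and by oral retinoid. No criterion for calling molecules alike is attached to it.
- The ranking threshold is written for countries only.

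**The case against.** The strongest reply is that the protocol contains no rule turning equal saturation into a finding of consistency. The only stated action for molecules is whether to add interviews, and saturation is the right measure for that. This stands, and it limits the point to the consistency statement.

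Second, content by molecule is foreseen elsewhere: section 9.2.2.2 plans grouping by specific oral retinoid, and code meaning is assessed at interim. This also stands. It would be wrong to say that the study as a whole cannot reveal differences between molecules. The gap lies in the interim comparison as worded.

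Third, the definition refers to a single codebook, and new codes are applied back to transcripts already coded. On a pooled reading, barriers specific to one molecule would surface as new codes. With 40 wholly different codes per molecule at assumed prevalences of 5% to 60%, the second molecule's 10 interviews would bring about 31.6 / (38.5 + 31.6) = 45% of the pooled codes. The simulation above therefore depends on the per-molecule reading. Section 9.2.3.2 does speak of saturation per molecule, but the protocol does not settle which reading applies.

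Fourth, section 9.2.3.2 defers detail to the Qualitative Analysis Plan, which is not shown. It may contain a content comparison. That would not correct the measure the protocol itself names, and the two should agree.

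A reader might also infer the reverse error: that molecules sharing the same barriers would be called different because one has 30 interviews and another 10. The documents do not support putting this forward as a main consequence. No passage treats unequal saturation as evidence of different barriers. Nor is the share of all possible codes ever seen what the criterion tests. With 40 codes spaced geometrically from 5% to 60%, expected new codes at the tenth interview are 0.96 out of 31.6 seen, or 3.0%, and the 10-interview group misses the 10% limit in only about 3% of runs (about 7% with prevalences of 3% to 50%). Higher miss rates need uniformly rare codes, such as 34% when every code has p = 0.05. In that case ten interviews really are too few, and adding interviews is the proper response.

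**Conclusion.** The mismatch between aim and measure is in the protocol's text and is not merely missing detail. Comparing code saturation between molecules can support a statement about whether each molecule had enough interviews. It cannot support a statement that barriers are consistent between molecules. Under the illustrative assumptions, with saturation judged per molecule, both molecules saturate in more than 99% of runs whether they share all their barriers or none. The exact rates rest on assumed code numbers and mention probabilities. That the measure does not respond to overlap follows from its definition under that reading.

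The sample-increase decision in the same paragraph is sound. The point concerns one interim statement and its wording, and it should be corrected before the interim analysis.

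**What to change.** In section 9.2.3.2, and in the Qualitative Analysis Plan so that the two agree:

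1. State that code saturation is used solely to decide whether a molecule needs more interviews, and whether it is judged on that molecule's own codes or on the pooled codebook.
2. Assess consistency on content. Tabulate, for each barrier, the number and share of participants reporting it by molecule, and compare the top-five rankings by molecule against an overlap criterion fixed before the interim analysis, as is done for countries.
3. Report the interview numbers (about 30, 10 and 10 adults at interim) beside the comparison. Repeating it with isotretinoin drawn down to 10 interviews is optional.

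The rankings are already to be collected and the transcripts coded, so the cost is revised wording and one table. The drawback is imprecision in the smaller groups. For a barrier reported by half of participants, and treating them as a simple random sample for illustration, the standard error is √(0.5 × 0.5 / 10) = 16 percentage points with 10 interviews and √(0.5 × 0.5 / 30) = 9 with 30. The table should be read as descriptive.
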